6.2.7. Patient Reported Outcomes endpoints

6.2.7.1. Sub-Study A

At each time point, the number and percentage of participants who complete the EORTC QLQ-C30 and EORTC QLQ-LC13 will be summarized, as will the reasons for non-completion of these measures. An instrument is considered complete if at least one item was answered by the participant.

Summary statistics (mean and standard deviation [SD], median, range, and 95% CI) of absolute scores will be reported using line charts for each of the functional, symptoms and overall quality of life subscales/items of the EORTC QLQ-C30 and the EORTC QLQ-LC13. The mean change from baseline with 95% CI will also be reported by time point. Line charts depicting the means and changes from baseline along with 95% CIs over time for each instrument will be produced.

6.2.7.2. Sub-Study B

There will be no analysis of PRO endpoints in Sub-Study B.

6.3. Other Endpoints

- Exploratory biomarker data will be analyzed based on the biomarker analysis sets as defined in Section 4 and as described in Section 6.2.5.

If data permits, appropriate descriptive statistics will be provided for the exploratory endpoints which will include DNA, RNA, and protein markers that may be relevant to the

- Depth of Response
- A Deep Response is defined as a confirmed response per RECIST v1.1 with a depth of response of at least 50%. The Deep response rate will be calculated along with the 2-sided 95% CI using the Clopper-Pearson method³ (exact CI for a binomial proportion as computed by default by the FREQ procedure using the EXACT option) by treatment group and based on the full analysis set.

6.4. Subset Analyses

Applicable to Phase 2 only.

Durable OR (Sub-Study A only) and OR will be summarized in the following subsets within each treatment group:

- Pooled Geographical Region
 - North America
 - Europe
 - Asia
 - Rest of World (ROW)
- Age
 - Age < 65 years
 - Age ≥ 65 years
- Gender
 - Male
 - Female
- Race
 - White
 - Asian
 - Black or African American
 - Other
- ECOG PS
 - 0
 - ≥1

6.5. Baseline and Other Summaries and Analyses

6.5.1. Baseline summaries

The following analyses will be based on the FAS overall and separately by Sub Study and treatment group.

6.5.1.1. Demographic characteristics

Demographic characteristics will be summarized by treatment group using the following information from the 'Screening/Baseline Visit' eCRF pages.

- Demographic characteristics
 - Gender: Male, Female
 - Race: White, Black or African American, Asian, American Indian or Alaska Native, Native Hawaiian or Other Pacific Islander, Other, Unknown
 - Ethnic origin:
 - Hispanic or Latino
 - Not Hispanic or Latino
 - Age (years): summary statistics
 - Age categories:
 - < 65 years, ≥ 65 years
 - < 65, 65-<75, 75-<85, ≥ 85 years
 - Pooled Geographical Region (as applicable):
 - North America
 - Europe
 - Asia
 - Rest of the World (Australasia, Latin America, Africa and/or Middle East will be included as additional pooled geographical regions if including > 10% of the overall treated population)
 - Geographic Region (as applicable):
 - North America
 - Latin America
 - Western Europe
 - Eastern Europe
 - Middle East
 - Australasia
 - Asia
 - Africa

– Eastern Cooperative Oncology Group (ECOG) Performance Status: 0, 1, 2, 3, and 4
Center codes will be used for the determination of the participant’s geographic region.

The listing of demographics and baseline characteristics will include the following information: participant identifier, treatment group, age, sex, race, ethnicity and ECOG performance status.

6.5.1.2. Medical history

Medical history will be coded using the most current available version of Medical Dictionary for Regulatory Activities (MedDRA) and will be summarized from the ‘Significant Medical History’ and “Medical History” eCRF page. Medical history will be summarized as the numbers and percentages of participants by MedDRA preferred term (PT) as event category and MedDRA primary system organ class (SOC) as summary category. Each participant will be counted only once within each PT or SOC.

Medical history will be displayed in terms of frequency tables: ordered by primary SOC and PT in alphabetical order.

6.5.1.3. Disease characteristics

Information on disease characteristics collected on ‘Primary Diagnosis’, ‘Substance Use’ and RECIST eCRF pages will be summarized overall and by treatment group. Summary statistics will be presented for the following.

From the ‘Primary Diagnosis’ eCRF page:

- Site of primary tumor
- Primary diagnosis (summarize all categories collected in the ‘Primary Diagnosis’ eCRF page)
- Time since initial diagnosis to date of first dose of study treatment (months), defined as (date of first dose of study treatment – date of initial diagnosis)/30.4375

From the RECIST eCRF page:

- Measurable disease (lesions) at baseline (Yes, No)
- Involved tumor sites at baseline

From the ‘Substance Use’ eCRF page:

- Smoking history (never smoker vs current vs former smoker)

Listing of disease history will be provided with all relevant data (as collected on the ‘Primary Diagnosis’ eCRF page) and derived variables as above. Brain metastasis at baseline will be reported as yes/no.

6.5.1.4. Prior anti-cancer therapies

The prior anti-cancer therapies are collected under the ‘Prior Cancer Therapy’, ‘Prior Radiation Therapy’ and ‘Prior Surgery’ eCRF pages.

The number and percentage of participants in each of the following anti-cancer therapy categories will be tabulated:

- Participants with at least one type of prior anti-cancer therapy
- Participants with at least one prior anti-cancer drug therapy
- Participants with at least one prior anti-cancer radiotherapy
- Participants with at least one prior anti-cancer surgery

Prior anti-cancer drug therapy will be summarized as follows based on the number and percentage of participants with the following:

- At least one prior anti-cancer drug therapy
- Number of prior anti-cancer drug therapy regimens: missing, 1, 2, 3, ≥ 4
- Prior anti-cancer immune therapy (including PD-1 and PD-L1)
- Intent of Drug Therapy: Neo-Adjuvant, Adjuvant, Advanced – Metastatic, Local regional Disease-Recurrence
- Best response: CR, PR, SD, PD, Unknown, Not applicable. Best response is derived from the last treatment regimen.

The prior anti-cancer drugs will also be summarized based on the number and percentage of participants by the drug class and preferred term. A participant will be counted only once within a given drug class and within a given drug name, even if he/she received the same medication at different times. The summary will be sorted on decreasing frequency of drug class and decreasing frequency of drug name in a given drug class. In case of equal frequency regarding drug class (respectively drug name), alphabetical order will be used.

Prior anti-cancer drug therapies will be included in the listing that follow with a flag to identify prior therapies. These will include the participant identification number, and all the relevant collected data-fields on the corresponding eCRF pages.

- Listing of anti-cancer drug therapies

6.5.2. Study conduct and participant disposition

The following analyses will be performed based on the FAS overall and separately by treatment group.

6.5.2.1. Participant disposition

The percentages below will be calculated based on the number of participants in the FAS.

- Total number of participants screened overall

- Number of participants who discontinued from the study prior to treatment with study drug overall and by the main reason for discontinuation
- Number and percentage of treated participants in each of the analysis sets defined in Section 4
- Number and percentage of participants with study drug ongoing (separately for each study drug administered in a combination)
- Number and percentage of participants who discontinued study drug overall and by the main reason for discontinuation of study drug (separately for each study drug administered in a combination)
- Number and percentage of participants who entered follow-up
- Number and percentage of participants who discontinued follow-up overall and by the main reason for discontinuation

In addition, the following will be summarized:

- Number and percentage of treated participants overall, by region (Europe, EEA (required by EudraCT), North America, Asia, Australia), by country within region
- Number and percentage of treated participants by center

A listing of participant discontinuations related to COVID-19 will be presented.

A listing of all participants affected by COVID-19 related study disruption by unique subject number identifier and by investigational site, and a description of how the individual's participation was altered.

6.5.2.2. Protocol deviations

All protocol violations that impact the safety of the participants and/or the conduct of the study and/or its evaluation will be reported. These include:

- Participants who are dosed on the study despite not satisfying the inclusion criteria
- Participants who develop withdrawal criteria whilst on the study but are not withdrawn
- Participants who receive the wrong treatment or an incorrect dose
- Participants who receive an excluded concomitant medication
- Deviations from GCP.

The identification of these and other CSR-reportable deviations will be based on the inclusion/exclusion criteria or other criteria presented in the protocol.

A listing of Protocol Deviations related to COVID-19 will be provided.

6.5.3. Study treatment compliance and exposure

The following analyses will be based on the safety analysis set by treatment group.

Exposure may be summarized as dose received (cumulative dose, actual dose intensity) and as dose received relative to intended dose (relative dose intensity [RDI]).

The information that will be summarized depends on how the study drug is dosed (e.g., infusion cyclical, oral daily, oral cyclical).

The formulae below should be applied to each study drug separately even when study drugs are administered in combination.

For Sub-Study A, the derivations below are provided assuming 1 cycle = 4 weeks and for the following study drugs:

- Sasanlimab administration: SC Q4W at a dose of 300 mg. Doses of sasanlimab may be recorded in the eCRF as 300 mg, 0 mg, or 'Unknown'. An 'Unknown' dose amount should not be considered a 0 mg dose and must be included in the derivations for first and last dose of study drug.
- Encorafenib administered orally QD PO as a dose of 300 or 450 mg in 4 week cycles.
- Binimetinib administered orally BID PO at a dose of 30 or 45 mg in 4 week cycles.

For Sub-Study B, the derivations below are provided assuming 1 cycle = 3 weeks and for the following study drugs:

- Sasanlimab administration: CCI at a dose of CCI. Doses of sasanlimab may be recorded in the eCRF as actual dose given in mg.
- Axitinib administered orally BID PO as a dose of 5 mg or 3 mg in 3 week cycles.
- SEA-TGT administered IV at a dose (mg/kg) of DL0, DL1, or DL-1 in 3 week cycles

6.5.3.1. Exposure to Sasanlimab

Sub-Study A: Duration of exposure to Sasanlimab (weeks) =

(last dose date of sasanlimab – first dose date of sasanlimab +28)/7

Sub-Study B: Duration of exposure to Sasanlimab (weeks) =

(last dose date of sasanlimab – first dose date of sasanlimab +21)/7

The median and range of non-zero doses of sasanlimab received by a participant will be provided.

The summary of exposure to sasanlimab will include:

- Duration of exposure to sasanlimab (weeks)

- Doses received for sasanlimab

6.5.3.2. Exposure to encorafenib

The dose level is calculated as actual dose administered (mg/day).

Intended duration of treatment with encorafenib (weeks) = (end date – date of first dose of encorafenib +1)/7,

where end date = date of last dose of **encorafenib**

Duration of exposure to encorafenib (weeks) =

(last dose date of **encorafenib** – first dose date of **encorafenib** + 1)/7

Cumulative dose is the sum of the actual doses of **encorafenib** received in the study.

Actual Dose Intensity (DI)

- Actual DI (mg/week) = [cumulative dose (mg)] / [intended duration of treatment (weeks)]

Relative Dose Intensity (RDI)

- RDI (%) = $100 \times [\text{cumulative dose}] / [\text{intended cumulative dose per week} \times \text{number of weeks from first dose of study drug to last dose of study drug}]$
= $100 \times [\text{cumulative dose}] / [7 \times d \times \text{duration of exposure to encorafenib (weeks)}]$

Where d= 300 mg or 450 mg

The summary of exposure to encorafenib will include:

- Duration of exposure to encorafenib (weeks)
- Cumulative Dose (mg)
- Actual DI (mg/week)
- RDI (%)

6.5.3.3. Exposure to binimetinib

The dose level is calculated as actual dose administered (mg/day).

Intended duration of treatment with binimetinib (weeks) = (end date – date of first dose of binimetinib +1)/7,

where end date = date of last dose of **binimetinib**

Duration of exposure to binimetinib (weeks) =

(last dose date of **binimetinib** – first dose date of **binimetinib** + 1)/7

Cumulative dose is the sum of the actual doses of **binimetinib** received in the study.

Actual Dose Intensity (DI)

- Actual DI (mg/week) = [cumulative dose (mg)] / [intended duration of treatment (weeks)]

Relative Dose Intensity (RDI)

- RDI (%) = $100 \times [\text{cumulative dose}] / [\text{intended cumulative dose per week} \times \text{number of weeks from first dose of study drug to last dose of study drug}]$
= $100 \times [\text{cumulative dose}] / [7 \times 2 \times d \times \text{duration of exposure to binimetinib in weeks}]$

where d= 30 mg or 45 mg

The summary of exposure to binimetinib will include:

- Duration of exposure to binimetinib (weeks)
- Cumulative Dose (mg)
- Actual DI (mg/week)
- RDI (%)

6.5.3.4. Exposure to axitinib

The dose level is calculated as actual dose administered (mg/day).

Intended duration of treatment with axitinib (weeks) = (end date – date of first dose of axitinib + 1)/7,

where end date = date of last dose of **axitinib**

Duration of exposure to axitinib (weeks) =

(last dose date of **axitinib** – first dose date of **axitinib** + 1)/7

Cumulative dose (mg) is the sum of the actual doses of **axitinib** received in the study.

Actual Dose Intensity (DI)

- Actual DI (mg/week) = [cumulative dose (mg)] / [intended duration of treatment (weeks)]

Relative Dose Intensity (RDI)

- RDI (%) = $100 \times [\text{cumulative dose}] / [\text{intended cumulative dose per week} \times \text{number of weeks from first dose of study drug to last dose of study drug}]$
= $100 \times [\text{overall cumulative dose}] / [7 \times 2 \times d \times \text{duration of exposure to axitinib in weeks}]$

where d= 5 mg or 3 mg

The summary of exposure to axitinib will include:

- Duration of exposure to axitinib (weeks)

- Cumulative Dose (mg)
- Actual DI (mg/week)
- RDI (%)

6.5.3.5. Exposure to SEA-TGT

The dose level is calculated as actual dose administered (mg/kg).

Intended duration of treatment with SEA-TGT (weeks) = (end date – date of first dose of SEA-TGT +21)/7,

where end date = date of last dose of SEA-TGT

Duration of exposure to SEA-TGT (weeks) =

(last dose date of SEA-TGT – first dose date of SEA-TGT +21)/7

Cumulative dose (mg/kg) is the sum of the actual doses of SEA-TGT received overall

Actual Dose Intensity (DI)

- Actual DI (mg/week/3-week cycle) = [cumulative dose (mg/kg)] / [intended duration of treatment with SEA-TGT (weeks)/3]

Relative Dose Intensity (RDI)

- Intended DI (mg/kg/3-week)=[intended cumulative dose per cycle]/[3-week cycle]=DLX (mg/kg/3-week cycle)
- RDI (%) = $100 \times [\text{actual DI}] / [\text{intended DI}] = 100 \times [\text{actual DI}] / [\text{DLX (mg/kg/3-week cycle)}]$

Where DLX is assigned dose of SEA-TGT in mg/kg (DL1, DL0, or DL-1)

The median and range of non-zero doses of SEA-TGT received by a participant will be provided.

The summary of exposure to SEA-TGT will include:

- Duration of exposure to SEA-TGT (weeks)
- Total number of infusions received for SEA-TGT
- Cumulative Dose (mg/kg)
- Actual DI (mg/kg/3-week cycle)
- RDI (%)

6.5.3.6. Dose reductions

Applicable to encorafenib (Sub-Study A), binimetinib (Sub-Study A), sasanlimab, axitinib (Sub-Study B) and SEA-TGT (Sub-Study B). Dose reduction is defined as a change to a non-zero dose level lower than that planned in the protocol.

Applicable to sasanlimab. In Sub-Study A the dose for sasanlimab in Sub-Study A can be entered as 0, 300 mg or ‘partial dose’. Where a ‘partial dose’ is captured as “UNK” on the sasanlimab CRF dosing page. The number and percentage of participants with at least one ‘partial dose’ dose amount as well as a breakdown of the number of unknown dose amounts (1, 2, 3, 4, 5, ≥ 6) will be summarized. In Sub-Study B, the actual dose for sasanlimab in mg is captured on eCRF and any non-zero dose less than planned **CCI** will be summarized as dose reduction.

The number and percentage of participants with at least one dose reduction as well as a breakdown of the number of dose reductions (1, 2, 3, ≥ 4) will be summarized.

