6.5.3.7. Dose interruptions

Applicable to encorafenib (Sub-Study A), binimetinib (Sub-Study A), and axitinib (Sub-Study B)

An interruption is defined as a 0 mg dose administered on one or more days for encorafenib, binimetinib, or axitinib. What follows defines how dose interruptions will be counted in the case of multiple dose interruptions.

- If an interruption occurs consecutively for at least two days, then it will be counted only once (example: If the actual dose on days 1-3 is 30 mg and actual dose on days 4-5 is 0 mg and dose interruption on days 4-5 is due to AE, then the total number of dose interruptions is 1).
- If an interruption occurs for more than one day but the days are not consecutive, ie there is at least one dosing day in between, then each dose interruption will be counted as a different occurrence (example: If the actual dose on days 1, 3 and 5, is 30 mg and actual dose on days 2 and 4 is 0 mg the total number of dose interruptions is 2).

A dose interruption is not considered a dose reduction.

The number and percentage of participants with dose interruptions and the corresponding reasons will be summarized.

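### Read literally, the SAP counts a day with one of two BID doses missed as a dose reduction for binimetinib or axitinib, while a missed once-daily encorafenib dose is an interruption

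*SAP*

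**What the plan says.** The relevant text is spread over several subsections of SAP 6.5.3.

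- **Schedules (6.5.3).** "Binimetinib administered orally BID PO at a dose of 30 or 45 mg in 4 week cycles". "Axitinib administered orally BID PO as a dose of 5 mg or 3 mg in 3 week cycles". "Encorafenib administered orally QD PO as a dose of 300 or 450 mg in 4 week cycles".
- **Dose level (6.5.3.2, 6.5.3.3, 6.5.3.4).** The same sentence appears for each oral drug: "The dose level is calculated as actual dose administered (mg/day".
- **Reduction (6.5.3.6).** "Dose reduction is defined as a change to a non-zero dose level lower than that planned in the protocol". No minimum duration, reason or prescriber decision is required. The table is to give "The number and percentage of participants with at least one dose reduction as well as a breakdown of the number of dose reductions", in the categories 1, 2, 3 and 4 or more.
- **Interruption (6.5.3.7).** "An interruption is defined as a 0 mg dose administered on one or more days for encorafenib, binimetinib, or axitinib". The section adds: "A dose interruption is not considered a dose reduction". Interruptions are to be reported with their reasons. Section 6.5.3.6 asks for no reasons for reductions.

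No rule in the SAP deals expressly with a day on which a participant takes only one of two BID doses.

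**The concern.** A dose-reduction table is normally read as showing how often the dose had to be lowered. If dose level means the milligrams actually taken in a day, a forgotten evening dose of a BID drug meets the definition: the day's total is non-zero and below plan. The same lapse with a once-daily drug gives 0 mg and goes into the interruption table. The class would then depend on dosing frequency and not on what happened to the prescription.

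Section 6.5.3.7 evidently means to keep skipped dosing out of the reduction count. For the BID drugs that separation works only when both doses of a day are skipped. The reduction counts for binimetinib (Sub-Study A) and axitinib (Sub-Study B) could therefore mix lowered prescriptions with ordinary missed doses. A reader who sets binimetinib beside encorafenib within the triplet would be comparing counts built differently.

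**Working it through.** The SAP gives no figure on this point, so there is none to reproduce. The check applies its definitions to one missed dose.

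**Rule as written.** Let D be the total taken on the day and P the planned daily total.
- D = 0: interruption (6.5.3.7).
- 0 < D < P: reduction (6.5.3.6, with dose level in mg/day from 6.5.3.2 to 6.5.3.4).

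**Inputs.** Doses and frequencies come from 6.5.3. P = dose × doses per day, and after one miss D = P − dose.

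| Drug and dose | P (mg/day) | D (mg/day) | Class under the literal rule |
|---|---|---|---|
| Binimetinib 45 mg BID | 90 | 45 | Reduction |
| Binimetinib 30 mg BID | 60 | 30 | Reduction |
| Axitinib 5 mg BID | 10 | 5 | Reduction |
| Axitinib 3 mg BID | 6 | 3 | Reduction |
| Encorafenib 450 mg QD | 450 | 0 | Interruption |
| Encorafenib 300 mg QD | 300 | 0 | Interruption |

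**RDI as a contrast.** RDI is built on cumulative dose and handles the same event sensibly. One missed binimetinib 45 mg dose in a week gives 100 × (7 × 90 − 45)/(7 × 90) = 100 × 585/630 = 92.9%.

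**How sensitive the count is (illustration only).** Assume each dose is missed independently with probability q, every miss is recorded, and the prescribed dose never changes. For a BID drug, the chance of exactly one miss on a day is 2q(1 − q). Over n days,

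P(at least one counted reduction) = 1 − [1 − 2q(1 − q)]^n.

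For q = 1% and n = 28: 2 × 0.01 × 0.99 = 0.0198, and 1 − 0.9802^28 = 0.429.

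| Assumed q per dose | 21 days (one Sub-Study B cycle) | 28 days (one Sub-Study A cycle) |
|---|---|---|
| 0.5% | 19% | 24% |
| 1% | 34% | 43% |
| 2% | 57% | 67% |
| 5% | 88% | 94% |

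Under the same assumptions, encorafenib has no counted reductions. Its misses appear as interruptions, with probability 1 − (1 − q)^28, which runs from 13% at q = 0.5% to 76% at q = 5%.

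The SAP supplies none of these rates. The table shows that a per-day rule is sensitive to occasional misses. It does not estimate what this trial will report.

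**The competing reading.** The worked examples in 6.5.3.7 use an actual dose of 30 mg on a dosing day. The planned daily totals are 60 or 90 mg for binimetinib, 6 or 10 mg for axitinib, and 300 or 450 mg for encorafenib. None is 30 mg, but 30 mg is one binimetinib administration at the lower dose. On a per-administration reading, a skipped BID dose would be a 0 mg record, hence an interruption and not a reduction. The dose-level sentence and this example therefore lead to different tables from the same data.

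**The case against.** The best defence is that 6.5.3.6 does not itself mention mg/day. Elsewhere in the SAP, dose level often means an assigned tier stated per administration, as in Table 4 (45 or 30 mg BID) and Table 5 (5 or 3 mg BID). On that sense, a forgotten evening dose changes no dose level. The 30 mg example in 6.5.3.7 points the same way. This has force: it shows that the literal outcome may not be intended. It does not remove the mg/day sentence, which 6.5.3.2 to 6.5.3.4 state for each oral drug, and 6.5.3.7 counts its interruptions by day. Two programmers could each defend a different table.

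Other objections stand and limit the point.

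- **Capture.** The effect arises only if single missed doses reach the dosing data. The SAP does not describe how the oral-drug eCRF records them.
- **Reach.** AEs leading to dose reduction come from the action-taken field on the AE eCRF page (6.6.1), so AE-driven reductions remain identifiable. RDI uses cumulative dose. No decision rule in 5.1.2 uses reduction counts.
- **Not strictly BID only.** A partly taken encorafenib daily dose would also be non-zero and below plan, and so a reduction.
- **Repeat misses.** A reader might infer that each further isolated miss adds to the 1, 2, 3, 4-or-more breakdown. Section 6.5.3.6 gives no counting rule for repeats, unlike 6.5.3.7, so this is only an inference.

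A reader might also infer that the plan demonstrably biases the reduction rate upward by a large amount. The documents do not support that. Any such figure needs a missed-dose rate, independence between doses and full recording of misses, and the SAP gives none of these.

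**Conclusion.** The point holds as a defect of definition. Followed literally, the SAP classes a day with one of two BID doses missed as a dose reduction for binimetinib or axitinib, and a missed encorafenib dose as an interruption. Its own 30 mg example suggests a different rule, so the sections need to be reconciled.

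The consequence is possible inflation of the descriptive reduction counts in 6.5.3.6 for the two BID drugs, by an amount the SAP does not allow to be estimated. It depends on how often single doses are missed and on whether the eCRF records them. If single misses are not captured, the inflation is nil. If they are, the illustration shows that even a low miss rate could matter. The AE-action tables, RDI and primary endpoints are not touched.

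**What to change.** Reconcile 6.5.3.2 to 6.5.3.4, 6.5.3.6 and 6.5.3.7 as follows.

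1. In 6.5.3.6, define a dose reduction for encorafenib, binimetinib and axitinib as a lowering of the prescribed dose per administration below the assigned level. Name the data source once the dosing eCRF has been checked. The SAP describes a dose-reduced action only on the AE page, so a matching field in the dosing record should not be assumed.
2. State that a day with a single missed BID dose is a missed dose and not a reduction. Report it on its own line where the eCRF captures it, and let the shortfall continue to count in cumulative dose and RDI.
3. In 6.5.3.7, say whether 0 mg refers to the day or to the single administration, and align the 30 mg examples with that choice.

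This changes an analysis definition only, not a dosing rule. It costs SAP wording and a small programming change. The downside is that reported reduction counts for the BID drugs will be lower than under the literal text.

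### Dose reductions are defined against the planned dose rather than the last dose taken, so a restart at an already reduced dose counts again in the 1, 2, 3, ≥4 breakdown

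*SAP*

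**What the plan says.** SAP section 6.5.3.6 covers encorafenib, binimetinib, sasanlimab, axitinib and SEA-TGT. Its general definition reads "Dose reduction is defined as a change to a non-zero dose level lower than that planned in the protocol". The dose taken just before the change is not mentioned. The section then asks for the number and percentage of participants with "at least one dose reduction as well as a breakdown of the number of dose reductions", in the categories 1, 2, 3 and ≥4.

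For sasanlimab in Sub-Study B the same section says that "the actual dose for sasanlimab in mg is captured on eCRF and any non-zero dose less than planned" (the planned dose is redacted) "will be summarized as dose reduction".

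Section 6.5.3.7 defines a hold of an oral drug: "An interruption is defined as a 0 mg dose administered on one or more days for encorafenib, binimetinib, or axitinib". It opens its rules for repeats with "What follows defines how dose interruptions will be counted in the case of multiple dose interruptions" and gives two worked examples. On the boundary between the two events it says only "A dose interruption is not considered a dose reduction". Section 6.5.3.6 has no corresponding rule for repeated reductions.

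**The concern.** A definition that compares with the planned dose is enough for a yes/no flag, because the first dose below plan sets the flag. It does not serve well for counting, because a count needs to know what the dose changed from.

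A participant who is reduced, held at 0 mg and then restarted at the same reduced dose makes a change, to a non-zero level, that is below plan. All the elements of the definition are met a second time. The sentence in section 6.5.3.7 removes the 0 mg days from the reduction count but says nothing about the restart.

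The breakdown would then mix true step-downs with restarts. Participants with repeated holds at a reduced dose would look as though their dose had been lowered repeatedly. The combination is foreseen in the plan: section 6.6.1.3 has tables of adverse events leading to both interruption and dose reduction of encorafenib, binimetinib and axitinib.

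**Working it through.** The plan states no reduction count to reproduce, so the check applies two counting rules to dose histories.

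**Inputs**
- Definition of a reduction and the count categories: section 6.5.3.6.
- A hold is a 0 mg dose, with two worked counting examples: section 6.5.3.7.
- Planned levels, encorafenib 300 or 450 mg QD and binimetinib 30 or 45 mg BID: section 6.5.3.

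**Rules.** Let P be the planned dose, d(1), d(2), … the successive doses, and d(0) = P.
- Literal rule: count each i with d(i) ≠ d(i−1) and 0 < d(i) < P.
- Step-down rule: count each i with d(i) > 0 and d(i) lower than the last preceding non-zero dose (P for the first).

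**Check of the coding.** The two interruption examples in section 6.5.3.7 (30-30-30-0-0 and 30-0-30-0-30 mg) come out as 1 and 2 interruptions, as the plan states.

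**One history step by step: encorafenib, P = 450, doses 450-300-0-300-0-300**
- 450 to 300: non-zero and below plan. Literal 1, step-down 1.
- 300 to 0: zero, not counted under either rule.
- 0 to 300: a change to a non-zero dose below plan. Literal 2. The last non-zero dose was 300, so step-down stays at 1.
- 300 to 0: not counted.
- 0 to 300: literal 3, step-down 1.

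**Results**

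| History (mg) | P | Literal | Step-down |
|---|---|---|---|
| 450-300-0-300 | 450 | 2 | 1 |
| 450-300-0-300-0-300 | 450 | 3 | 1 |
| 450-300-0-300-0-300-0-300 | 450 | 4 (top category) | 1 |
| 45-30-0-30-0-30 | 45 | 3 | 1 |
| 30-0-30-0-30 (pattern of the plan's second example) | 45 | 3 | 1 |
| 30-0-30-0-30 | 30 | 0 | 0 |
| 450-0-450 | 450 | 0 | 0 |
| 450-300-450 | 450 | 1 | 1 |
| 450-300-(a level below 300)-300 | 450 | 3 | 2 |

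In these histories the excess of the literal over the step-down count equals the number of restarts at an unchanged below-plan dose plus the number of increases to a level still below plan. It is zero when the participant resumes at, or returns fully to, the planned dose. Whether the count is at least 1 is the same under both rules in every row.

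The last row is conditional. The SAP lists neither within-participant levels below 300 mg nor a rule on going back up; both would sit in the protocol. The restart rows need no such assumption.

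**Sasanlimab, Sub-Study B.** Suppose, for illustration, one step down kept for five cycles. Counted as a change it is 1 reduction; counted per administration below plan it is 5. The sentence does not say which applies.

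**The case against.** The strongest reply is that the term defined is a reduction and that section 6.5.3.7 treats the hold as a separate event. A programmer could then sensibly read 300-0-300 as one reduced level with one hold. That reading is available, and some tables would be programmed that way. It is not what the definition says, however, and two programmers following the section could produce different breakdowns. The plan did not leave the parallel question for interruptions to judgement. In section 6.5.3.8 it also already measures delay between consecutive non-zero doses, which is the comparator needed here.

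Three stronger readings are tempting, and the document does not support them:
- A reader might infer that every restart after a hold is counted. A restart at the planned dose is not; 450-0-450 gives 0.
- A reader might infer that increases will in fact be reported as reductions. That requires at least two levels below plan and permission to go back up, and the SAP shows neither.
- A reader might infer that the Sub-Study B sentence makes each below-plan sasanlimab dose a separate reduction. It says which doses qualify, not how repeats are counted. If such doses are incomplete administrations, a count per administration may be the useful one.

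It is also fair to say that reduced dosing is described elsewhere without this count. Cumulative dose, actual dose intensity and relative dose intensity (sections 6.5.3.2 to 6.5.3.5) use doses received. The adverse event tables for dose reduction (sections 6.6.1 to 6.6.1.2) use the action recorded on the adverse event page.

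**Conclusion.** The point holds as a minor one. The definition in section 6.5.3.6, taken as written, gives a wrong number of reductions for any participant who restarts at an already reduced dose after a 0 mg hold: 3 against 1 after two such restarts, and 4 against 1, the top category, after three. This rests on the literal wording and on section 6.5.3.7 recording a hold as 0 mg.

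The effect is confined to the descriptive breakdown by number of reductions. The number of participants with at least one reduction, the dose-intensity summaries, the adverse event tables and every efficacy endpoint and decision rule are untouched. The histories above are constructed for single participants. The SAP gives no basis for estimating how often restarts below plan will occur, so the size of the distortion in the table cannot be stated.

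**What to change.** In section 6.5.3.6, keep the comparison with plan for the flag of at least one reduction. For the count, add that a reduction is a move to a non-zero dose below the last non-zero dose taken, with the assigned dose as comparator for the first one. State that resuming at the same level after 0 mg is not a new reduction. If the protocol permits increases to a level still below plan, state that these are not counted either.

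For sasanlimab in Sub-Study B, state whether below-plan doses are counted per administration or per step-down, and label the table to match.

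The cost is one or two sentences and a small programming change. No new data are needed, and no dosing rule is altered.
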